3.4.3.2 Secondary Objectives Analyses

Crosstab analysis of Did parents wake to assist child when alarm goes off: yes or no (2 nd measure of compliance)
 Logistic regression analyses of What is the role of parental assistance in Dry night rates
 Role of familial nocturnal enuresis in treatment outcomes
 Logistic regression analysis of spontaneous age remission of enuretic parents to the success of the alarm therapy.
 Crosstab analysis of Parents comparing enuretic parents vs non enuretic parents and success with alarms.

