2.1.2 Device Clinical Experience

Data to be presented at the American urological association meeting scheduled for Sept 10, 2021 based on quality Improvement study

Abstract ID: 21-3995

Abstract Title: A Novel Bedwetting Alarm Utilizing Real Time Heart Rate Analysis and Artificial Intelligence to Wake Patients Prior to Wetting: Preliminary Outcomes

Presenting Author: [name]

Session Details

Type: Podium - PD15

Title: Pediatric Urology I

Date: Friday, September 10, 2021

Time: 3:30 PM - 5:30 PM

Building: Venetian-Sands Expo Center

Room: Marco Polo 804

A copy of the abstract is attached below

21-3995

A NOVEL BEDWETTING ALARM UTILIZING REAL TIME HEART RATE ANALYSIS AND ARTIFICIAL INTELLIGENCE TO WAKE PATIENTS PRIOR TO WETTING: PRELIMINARY OUTCOMES

[name]*, New Haven, CT, [name], [name], [name], Ashland, VA

INTRODUCTION AND OBJECTIVE: Bedwetting alarms (BWA) have been around for more than half a century with little innovation in the field. GOGOBand® utilizes real time heart rate variability (HRV) analysis and applied artificial intelligence (AI) to create an alarm that is capable of waking the patient up prior to wetting. Our Aim was to evaluate the efficacy the new Smart GoGoBand®.

METHODS: Data was retrieved and analyzed from our servers, of patients who purchased the GOGOBand® which includes a heart rate monitor, moisture sensor, bedside tablet and app for the parents phone in this study. There are 3 modes, training; where the individualized HRV parameters are used to build the alerting model. Once patients are done with training, they enter the Predictive mode where they receive an alarm if an impending urination event is noted. In Weaning mode the alerting is gradually suppressed. Only patients that used the alarm for more than 30 days were included. Data analysis was done with SPSS and xistat.

RESULTS: A total of 40 subjects that have used the system for more than 30 nights were included in this analysis. Gender mix was 33 males (82.5%) and 7 females (17.5%). The mean age of the subjects is 10.6 yrs. Subjects wet the bed an average of 6.2 nights per week prior to treatment. Severity and number of accidents per night had no impact on the ability to achieve dryness with the GOGO Band® device in logistical regression analysis. The data was also segregated based on compliance since it became clear during the analysis that compliant patients achieved better results than non-compliant patients.

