5.2.2 Secondary and Exploratory Outcome Variables (if applicable)

Did parents wake to assist child when alarm goes off: yes or no (2 nd measure of compliance)

What is the role of parental assistance in Dry night rates.

Evaluate parental nocturnal enuresis rates as children and cessation of enuresis and compare to final success outcomes of participants.

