6.1 Treatment – Device

6.1.1 Intended Use for Device (provide the following information for each device being investigated in the study)

Generic bedwetting alarms

Generic bedwetting alarms which are commercially available and are an FDA class II device
See below the FDA documentation on enuresis alarms

[Code of Federal Regulations]
[Title 21, Volume 8]
[Revised as of April 1, 2020]
[CITE: 21CFR876.2040]

TITLE 21--FOOD AND DRUGS
CHAPTER I--FOOD AND DRUG ADMINISTRATION
DEPARTMENT OF HEALTH AND HUMAN SERVICES
SUBCHAPTER H - MEDICAL DEVICES

PART 876 -- GASTROENTEROLOGY-UROLOGY DEVICES

Subpart C - Monitoring Devices

Sec. 876.2040 Enuresis alarm.

(a) *Identification.* An enuresis alarm is a device intended for use in treatment of bedwetting. Through an electrical trigger mechanism, the device sounds an alarm when a small quantity of urine is detected on a sensing pad. This generic type of device includes conditioned response enuresis alarms.

(b) *Classification.* Class II (special controls). The device is exempt from the premarket notification procedures in subpart E of part 807 of this chapter subject to § 876.9.

[48 FR 53023, Nov. 23, 1983, as amended at 63 FR 59228, Nov. 3, 1998]

GoGoband® is a FDA class II device

GoGoband® is a biometric, artificial intelligence and machine learning powered wearable bedwetting alarm uses of heart rate data, heart rate variability (HRV) analysis and real time monitoring that combines the use of algorithms developed with machine learning to learn the individual profile of each patient. Each device consists of a photoplethysmography (PPG) heart rate sensor worn on the calf, a beside tablet, a Bluetooth moisture sensor and a parent app that can alarm the parent that a wetting event is eminent or has occurred.

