3.2 Assessments

3.2.1 Efficacy

SNEA: Device Will be provided to the patient

1. A log will be kept document that the patient wore the device that night
2. Mark if they were wet or dry that morning
3. if the alarm sounded that night
4. whether the device was on the patient in the morning
5. A log will be kept if the patient took ibuprofen or any Ansaïd that day

GoGoband®: Device Will be provided to the patient

1. A log will be kept identifying that the patient wore the device that night
2. Mark if they were wet or dry that morning
3. if the alarm sounded that night
4. whether the device was on the patient in the morning
5. A log will be kept if the patient took ibuprofen or any ansaid that day

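### At night level the parental-assistance regression is biased or barely estimable, because assistance exists only when an alarm sounds and the standard alarm sounds after urine is present

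*Combined protocol and SAP*

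**What the plan says.** Section 5.2.2 lists as a secondary or exploratory variable "Did parents wake to assist child when alarm goes off: yes or no", described as a second measure of compliance, and also asks about the role of parental assistance in dry-night rates. Section 3.4.3.2 gives the analysis in one line: "Logistic regression analyses of What is the role of parental assistance in Dry night rates".

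The two devices trigger differently. The regulatory description of enuresis alarms in section 6.1.1 says "the device sounds an alarm when a small quantity of urine is detected on a sensing pad". The same section describes GoGoband as having "a parent app that can alarm the parent that a wetting event is eminent or has occurred". Section 2.1.2 says that in predictive mode "they receive an alarm if an impending urination event is noted".

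In both arms section 3.2.1 logs the outcome each day ("Mark if they were wet or dry that morning") and, separately, whether the alarm sounded. The other listed items are device wear that night, "whether the device was on the patient in the morning", and ibuprofen or similar drugs. Parental waking is not listed. Appendix 2 is an alarm log, but the form is not reproduced.

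Section 3.4.3.2 states no unit of analysis, no coding for nights without an alarm, no restriction to alarm nights, no arm term and no allowance for repeated nights. Section 3.4.4 (Subsets and Covariates) has no text.

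**The concern.** A parent can be recorded as assisting only on a night with an alarm. With the standard alarm, such a night is by design one on which urine has already been passed. If exposure and outcome are taken from the same night, wetting causes the alarm and the alarm makes assistance possible, so the regression describes the trigger and not the parent. GoGoband can alarm before voiding, so an assisted night there can be dry, and the same yes/no item relates to wetting differently in each arm.

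The report could therefore state that parental help lowers dryness, or that it works differently with the two devices, when neither is true. Families and clinicians could act on either statement.

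**Working it through.** **The plan's own figure.** None is given for this analysis. The only calculation is the main sample size: (0.25 + 0.16) × ((1.645 + 0.842)/0.3)² = 28.2, rounded up to 29 per group. It reproduces the stated 29 and has no bearing here.

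**Inputs.** From the documents: the definitions above, 90 nights per child (section 5.1.1) and 50 children per arm (section 5.3.1). The documents give no rates for assistance, false alarms or missed alarms, so these are assumed. Assistance has no effect on any night. The mean chance that a parent wakes to an alarm is A = 0.5, independent of the child. The mean chance of a night without a voiding event is d = 0.5.

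**1. SNEA, all nights, no-alarm nights coded as no assistance.** Let e be both the false-alarm and the missed-alarm rate.

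- P(alarm) = d·e + (1 − d)(1 − e) = 0.5 for every e, since d = 0.5
- P(dry | assisted) = d·e / P(alarm)
- P(dry | not assisted) = (d − d·e·A) / (1 − A·P(alarm))

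| e | Dry, assisted | Dry, not assisted | Odds ratio |
|---|---|---|---|
| 0 | 0 | 0.5/0.75 = 0.667 | 0 (complete separation) |
| 0.05 | 0.025/0.5 = 0.05 | 0.4875/0.75 = 0.65 | 0.0526/1.857 = 0.03 |
| 0.10 | 0.05/0.5 = 0.10 | 0.475/0.75 = 0.633 | 0.111/1.727 = 0.06 |

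A simulation (50 children, 90 nights, 300 replicates, child dry-night logit N(0,1), assistance Beta(2,2)) gave 0, 0.029 and 0.065.

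**2. GoGoband, same coding.** Let π be the chance that an impending event is predicted, w the chance that a predicted event is averted, and f the false-alarm rate on event-free nights. Unpredicted events end wet, with a moisture alarm.

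- P(alarm) = 0.5 + 0.5f
- P(alarm and dry) = 0.5πw + 0.5f
- P(dry) = 0.5 + 0.5πw

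With π = 0.5, w = 0.8, f = 0: dry if assisted 0.2/0.5 = 0.40; dry if not (0.7 − 0.1)/0.75 = 0.80; odds ratio 0.667/4 = 0.17. With π = 0.9, w = 0.9, f = 0.3: 0.555/0.65 = 0.854 against (0.905 − 0.2775)/0.675 = 0.930; odds ratio 0.44 (simulated 0.445). Three other scenarios, with π up to 0.97 and w up to 0.98, simulated at 0.29 to 0.37. The artefact is present in both arms and differs in size.

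**3. Alarm nights only.** The simulated odds ratio is 0.99 to 1.01 wherever the outcome varies. In SNEA only about 5% or 10% of alarm nights are dry (e = 0.05 or 0.10). With an error-free alarm none is, and the effect cannot be estimated.

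**4. One record per child, no true effect.**

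| Exposure | Assumptions | Correlation with dry rate |
|---|---|---|
| Assisted nights, every wet night alarms | mean dry rate 0.8, ICC 0.3 | −0.85 |
| Same | mean 0.5, ICC 0.1–0.3, three spreads of assistance | −0.40 to −0.72 |
| Same, SNEA with 0–10% alarm error | logit-normal, mean 0.5 | −0.56 to −0.65 |
| Same, GoGoband scenarios of step 2 | logit-normal event rate | −0.32 to −0.62 |
| Share of alarm nights assisted | the mean-0.8 and logit-normal settings above | about 0 |

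**5. Cost of an early exposure window.** Take the dry probability per child as Beta(a, b) with a + b = (1 − ICC)/ICC, constant over nights, and an alarm on every wet night. The chance of no alarm in nights 1–30 is the product over k = 0 to 29 of (a + k)/(a + b + k). For mean 0.8 and ICC 0.3, a = 1.867 and b = 0.467, which gives 25%; 44% have two alarms or fewer. For mean 0.5 it is 0.03% at ICC 0.1 (a = b = 4.5) and 2.3% at ICC 0.3 (a = b = 1.167).

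**The case against.** A reader might infer that the planned regression must show parental help to be harmful. The documents do not support that. Section 3.4.3.2 is one line and leaves the coding open, and section 5.2.2 words the item conditionally on an alarm. Used that way, the alarm-night odds ratio is about 1, and the child-level share of alarms assisted is not distorted. This stands: harm appears only if no-alarm nights count as unassisted or if assisted nights are counted. It does not rescue a night-level analysis, because the conditional version leaves almost no outcome variation in SNEA.

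A reader might also infer that every assisted SNEA night must be wet, so that the odds ratio is exactly 0. That needs an error-free alarm. Wet or dry and alarm sounded are separate log items, the trigger is a small quantity of urine, and that trigger text is the generic regulatory description. With 5-10% error the figure is 0.03 to 0.07, which is still severe.

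The correlations rest wholly on assumed rates. Their size moves with those rates, but the direction did not change in any setting tried.

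Section 3.2.1 may not list everything on the form, so the absence of a parental-waking item from the log is not established.

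Finally, the only stated secondary objective (section 4.3) is familial incidence; parental assistance sits under secondary and exploratory variables. That limits the importance of the point but does not remove it, since the analysis is named and planned.

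**Conclusion.** The concern holds in a conditional form. A night-level fit is either strongly biased towards harm (no-alarm nights coded as no assistance: odds ratio near 0 in SNEA, 0.17 to 0.45 in the GoGoband scenarios) or close to inestimable in SNEA (alarm nights only). Counting assisted nights per child carries the same bias: about −0.4 to −0.85 when every wet night alarms, and as weak as −0.32 in GoGoband. Of the exposures examined, only the child-level share of alarm nights assisted is both estimable in SNEA and free of this artefact, and the plan does not specify it.

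That the alarm follows urine in one arm and can precede it in the other comes from the documents. All sizes rest on assumed rates. The primary device comparison does not depend on this analysis.

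**What to change.** In section 3.4.3.2, replace any night-level regression with one record per child:

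- **Exposure:** the share of that child's alarm nights on which a parent woke. Section 3.2.1 already logs whether the alarm sounded, so the denominator exists.
- **Outcome:** the child's dry-night share, or cure as already defined.
- **Model:** adjust for pre-treatment wet nights, which the improvement outcomes need anyway, and report by arm. One record per child also removes the clustering of nights.
- **Timing, preferably:** exposure from an early window and outcome from a later one, for example nights 1–30 and 61–90, so that assistance precedes the dryness it is meant to explain.
- **Log:** check the alarm log in Appendix 2, and add a yes/no column for parental waking if it is absent.

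The cost is a few sentences in the plan and at most one log column. The early window has a real downside: children with few or no early alarms have a noisy or undefined exposure. About 25% would have none in nights 1–30 at a mean dry rate of 0.8 and ICC 0.3, and almost none to 2% at a mean of 0.5. These children must be described separately, and the outcome then uses only the later nights. The result remains an observational association, because parents who wake may differ in other ways.

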4.3 Secondary Objectives (if applicable)

To ascertain if familial incidence of nocturnal enuresis has an effect on outcomes

5 Study Design

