5.3.2 Eligibility Criteria/Vulnerable Populations

In order to be eligible to participate in this study, an individual must meet all of the following criteria:

1. Provision of signed and dated informed consent form
2. Stated willingness to comply with all study procedures and availability for the duration of the study

3. Male or female, aged 6 to 21 years
4. In good general health as evidenced by medical history and diagnosed with MNE
5. Ability to and be willing to adhere to the treatment regimen.
6. Subjects to be eligible for the Trial need to have functioning WiFi at home utilizing a home network and not a cellular tethering connection.

An individual who meets any of the following criteria will be excluded from participation in this study:

1. No patient may have had treatment of MNE in the past 6 months whether with medications or alarms
2. Current use of on ADHD medications, Tricyclics, SSRI's, NRI's or any antipsychotic medications.
3. Presence of Autistic Spectrum disorder, ADHD, genetic syndrome associated with developmental or learning disabilities
4. Treatment with another investigational drug or other intervention within last 6 months
5. Any form of Diabetes Mellitus or Diabetes Insipidus
6. No patient with known Chronic renal disease with moderate to severe renal impairment (defined as a creatinine clearance below 50mL/min).
7. No patient with known hyponatremia or a history of hyponatremia.

6 Methods

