3.4.3 Planned Analysis

3.4.3.1 Primary Analyses

Outcomes will be evaluated between the 2 groups using crosstab analysis of the data for the following data :

Wetting event: Dry or Wet

Did patient wear the device: yes or no used to measure compliance

Did patient take the medication: yes or no used to measure compliance
 Is the patient considered cured (dry 29/30 nights) : yes or no
 Is the patient partially better (improvement of 50% or more compared to pretreatment)
 Does the patient show no improvement (<50% improvement compared to Pretreatment)
 Logistic regression analysis may be performed on the incremental wet dry data vs time to achieving dryness

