3.4.3.4 Analysis of Subject Characteristics

Age and sex of patients in each group
 Dvq scores of each group

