3.4.3.5 Interim Analysis (if applicable)

interim analysis will be done a midpoint to evaluate ages of groups so we can make adjustments to have an age matched cohort.

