3.4.3.7 Other

3.4.4 Subsets and Covariates

3.4.5 Handling of Missing Data

Patients who drop out of the study will be considered failures for purposes of the study with regards to success vs partial or failure analysis
 Dry /wet night rates will be maintained for the overall analysis of overall dry/wet ratios regardless of the patient ceases participation

4 Trial Administration

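### The familial-enuresis analyses name neither the child's age nor the treatment arm, so confounding by age is left uncontrolled for the only stated secondary objective

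*Combined protocol and SAP*

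**What the plan says.** Section 4.3 states one secondary objective: "To ascertain if familial incidence of nocturnal enuresis has an effect on outcomes". Section 3.4.3.2 gives two analyses that bear on it directly:

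- "Crosstab analysis of Parents comparing enuretic parents vs non enuretic parents and success with alarms"
- "Logistic regression analysis of spontaneous age remission of enuretic parents to the success of the alarm therapy"

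It also lists the role of familial enuresis as a topic, without a model. None of these lines mentions the child's age, the treatment arm or an interaction. The place where covariates could have been named, "3.4.4 Subsets and Covariates", is a heading with nothing under it.

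The eligible population in section 5.3.2 is "Male or female, aged 6 to 21 years". Age appears in three other places. Section 3.4.3.4 describes "Age and sex of patients in each group". The randomisation text after section 6.1.2 plans an effort to match the groups on age once half of either group is enrolled. Section 3.4.3.5 says "interim analysis will be done a midpoint to evaluate ages of groups so we can make adjustments to have an age matched cohort". All three concern the two device groups.

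**The concern.** Randomisation balances the devices. It does not balance children with and without an enuretic parent, or children of early- and late-remitting parents. Those comparisons are observational even though they sit inside a randomised trial, and matching the device groups on age does nothing for them.

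There is a plausible route to confounding. Section 5.3 enrols only children who still wet at least twice a week. If age at remission runs in families, which is the idea behind the planned regression, an older child who is still wetting will tend to come from a later-remitting family. Parental remission age is then tied to the child's age. If age also affects how well alarms work, an analysis that omits age credits part of its effect to the family, or cancels a real familial effect. A published statement that family history does or does not affect alarm response would then be hard to interpret.

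Arm raises a different issue. The plan expects success to differ substantially between devices, and an analysis without arm cannot show whether family history matters for one device only.

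**Working it through.** **Inputs from the documents.** Planned success is 0.5 (SNEA) and 0.8 (GoGoband), allocation 1:1 (section 3.4.2). There are 100 children, 50 per arm (section 5.3.1; the synopsis says 150). Ages are 6 to 21 (section 5.3.2). Section 3.4.3.2 does not define success; section 3.4.3.1 offers, among others, "Is the patient considered cured (dry 29/30 nights) : yes or no".

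**The plan's own figure.** None is given for the secondary analyses. The primary sample size confirms how 0.5 and 0.8 are used: (1.645 + 0.842)² × (0.5×0.5 + 0.8×0.2) / 0.3² = 28.2, so 29, which matches the stated 29 if read as per group.

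**Assumptions, because the documents give no figures.** Half of the children have an enuretic parent. The age gap between parental-history groups, the correlation of child's age with parental remission age, and the odds ratio (OR) for success per SD of child's age are varied as shown.

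**Model.** The true familial effect is zero. The odds of success at mean age are 0.5/0.5 = 1 and 0.8/0.2 = 4, so logit(success) = log 4 × [GoGoband] + log(OR per SD) × age in SD. Each cell has 2,000 runs with a two-sided 5% test. Monte Carlo standard error near 5% is √(0.05×0.95/2000) ≈ 0.5 points.

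False-positive rates for the familial term:

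| Analysis | Link of age to parental variable | OR for success per SD of age | Without age or arm | With age and arm | Median OR without age or arm |
|---|---|---|---|---|---|
| Parental enuresis yes/no, n=100 | gap 0.3 SD | 1.5 / 2.0 | 5.2% / 6.1% | 4.5% / 5.6% | 1.10 / 1.20 |
| same | gap 0.5 SD | 1.5 / 2.0 | 6.3% / 9.9% | 5.0% / 5.5% | 1.19 / 1.35 |
| same | gap 0.8 SD | 1.5 / 2.0 | 11.0% / 19.0% | 4.6% / 4.8% | 1.32 / 1.65 |
| Remission age, n=50 | correlation 0.3 | 1.5 / 2.0 | 5.4% / 8.3% | 4.0% / 4.8% | 1.12 / 1.19 (per SD) |
| same | correlation 0.5 | 1.5 / 2.0 | 7.5% / 14.2% | 5.1% / 5.1% | 1.21 / 1.35 (per SD) |

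When either age link is absent, the rate without age or arm is 3.8% to 4.8%. Both links are needed for bias.

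**How strong could the first link be?** A simulation of enrolment while still wetting, with an assumed parent-child correlation in remission age of 0.3 to 0.7 and presentation age uniform from 6 to 21, gave a correlation of 0.13 to 0.35 between child's age and parental remission age. The correlation-0.5 rows therefore lie above what that mechanism alone produced.

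**Does arm matter for the bias?** No. Adding arm without age in the worst yes/no cell moved the rate from 19.0% to 21.0%.

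**What leaving arm out does cost.** Suppose parental history truly had an OR of 2 within each device (an illustration). Success without the history is 0.5 and 0.8, mean 0.65; with it, 0.667 and 0.889, mean 0.778. The OR ignoring arm is (0.778/0.222) / (0.65/0.35) = 3.50/1.857 ≈ 1.88, a modest pull towards 1.

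**Information available.** Expected failures at N=100 are 50×0.5 + 50×0.2 = 25 + 10 = 35. With half in each history group and no association, the variance of the log OR is 4/12.5 = 0.32 for SNEA and 2/5 + 2/20 = 0.50 for GoGoband.

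- Common familial OR: variance 1/(1/0.32 + 1/0.50) = 0.195, so the 95% interval is the estimate times or divided by exp(1.96×0.442) ≈ 2.4.
- Arm-by-history ratio: variance 0.32 + 0.50 = 0.82, so times or divided by exp(1.96×0.906) ≈ 5.9.

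**The case against.** The strongest reply is that the plan is silent rather than wrong. A crosstab can be layered and a logistic regression can carry covariates, so a reader who infers that the arms are pooled, or that the regression has one predictor, is reading silence. That stands: pooling is the natural sense of the text but is not written. It does not remove the point, because the empty section 3.4.4 leaves nothing to commit the analyst to an adjusted model.

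The second reply is that neither age link is documented. That also stands. The plan's age matching shows concern for balance between devices; it is not evidence that age predicts success. Where the links are modest, the false-positive rate stays close to nominal. Steeper assumptions give larger figures: with 70 children who have an enuretic parent, correlation 0.5 and 0.3 log-odds per year, the rate was about 30%. But 0.3 per year over ages 6 to 16 means a success OR of e³ ≈ 20 between youngest and oldest, which nothing in the documents supports.

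A reader might also infer from the crosstab's wording that parents are the unit of analysis, so that a child with two parents is counted twice. The documents do not support this: success belongs to the child, and section 5.2.2 compares parental history with the participants' outcomes. What is missing is how two parents' remission ages become one value.

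Finally, these are secondary and exploratory analyses, and the device comparison does not depend on them.

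**Conclusion.** The point holds as a limited one. As written, the familial analyses do not control for the child's age, over a wide age range and for an exposure that is not randomised, so confounding by age cannot be excluded. Its possible size is a false-positive rate from about 5% (no real harm) to about 19%, against a nominal 5%, with a null OR appearing as roughly 1.1 to 1.65 for parental history. Adjustment returns the rate to about 4% to 6%. The range rests wholly on assumed age links and an assumed 50% share with an enuretic parent.

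Two stronger conclusions might be inferred and should not be. One is that a familial finding would be only an age effect: that needs both links, and the documents show neither. The other is that omitting arm produces the bias: arm is randomised, hence independent of parental history in expectation, and its omission costs only some efficiency and the ability to see a device-specific association.

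**What to change.** Replace the two familial analyses in section 3.4.3.2 with one child-level logistic regression of a named success outcome on parental enuresis, adjusted for treatment arm and child's age, reporting ORs with 95% confidence intervals. Fit the remission-age model in the same way among children with an enuretic parent, and state in advance which single parental value is used when both parents were enuretic. Enter arm and child's age under section 3.4.4. Keep the crosstab as description if wanted. Label any arm-by-parental-history term exploratory, since about 35 expected failures at N=100 cannot estimate it usefully.

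The cost is a change of wording and a slightly more complex model. Arm and child's age are already recorded, and the parental data are those the plan's own analyses already require.
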